## Acronyms

AE	Adverse event
AIDS	Acquired Immune Deficiency Syndrome
ALT or SGPT	Alanine transaminase or serum glutamic-pyruvic transaminase
ART	Antiretroviral therapy
ARV	Antiretroviral
AST or SGOT	Aspartate transaminase or serum glutamic oxaloacetic transaminase
CDC	Centers for Disease Control and Prevention
CI	Confidence Interval
CM	Cryptococcal meningitis
CNS	Central nervous system
CRA	Clinical research associate
CrAg	Cryptococcal antigen
CRF	Case reporting form
CSF	Cerebrospinal fluid
DEFF	Design effect
DOB	Date of birth
EFV	Efavirenz
ELISA	Enzyme-linked immunosorbent assay
HIV	Human Immunodeficiency Virus
HRQOL	Health-related quality of life
ICC	Intraclass correlation coefficient
ICER	Incremental cost-effectiveness ratio
ID	Identification
IRB	Institutional Review Board
IRIS	Immune reconstitution inflammatory syndrome
LFA	Lateral flow assay
LNMP	Last Normal Menstrual Period
LP	Lumbar puncture
MOH	Ministry of Health
NHTD	National Hospital for Tropical Diseases
NVP	Nevirapine
OI	Opportunistic infection

## Cryptococcal Retention In Care Study (CRICS)

OPC	Outpatient clinic
OUCRU	Oxford University Clinical Research Unit in Vietnam
PC	Personal computer
PEPFAR	President's Emergency Plan for AIDS Relief
PI	Principal Investigator
PLHIV	People Living with HIV
POC	Point of contact
QALY	Quality-adjusted life-year
SAE	Serious adverse event
SOC	Standard of care
SOP	Standard Operating Procedure
TB	Tuberculosis
TDH	Tropical Diseases Hospital
TmAg	Talaromyces marnieffei
USD	United States Dollar
VAAC	Viet Nam Administration of HIV/AIDS Control
WHO	World Health Organization

## Protocol Summary

**Title:** Vietnam Cryptococcal Retention in Care Study (CRICS).

**Purpose:** This is a multicenter prospective cohort evaluation of the implementation of a cryptococcal antigen (CrAg) screening program at selected outpatient HIV clinics (OPCs) and network laboratories in Vietnam. The project will be implemented in 2 phases;

**Phase 1:** From August 2015 to March 2017 [projected], HIV-infected patients who present for HIV care and undergo CD4 testing will be reviewed to determine the proportion of newly presenting patients with advanced disease ( $CD4 \leq 100 \text{ cells}/\mu\text{L}$ ). Reflex CrAg screening will be performed using Lateral Flow Assay (LFA) for those with  $CD4 \leq 100 \text{ cells}/\mu\text{L}$ , per Vietnam national guidelines.

Patients with  $CD4 \leq 100 \text{ cells}/\mu\text{L}$  who present for ART at a study OPCs—CRICS Sites—will be recruited into the longitudinal study and followed up with assessments and the collection of routine and supplemental data for 12 months or through September 2017 (whichever comes sooner). Those who are CrAg-positive, but have no features of central nervous system (CNS) disease, will be treated with high-dose fluconazole. Those with symptoms of CNS disease will be treated according to national guidelines. Survival, retention in care, and other clinical outcomes will be documented for patients who test CrAg-positive and are treated with fluconazole and those who test CrAg-negative. Data from those tested at participating labs but not eligible for enrollment in the longitudinal study will contribute to estimation of the prevalence of CrAg.

**Phase 2:** From April 2017[projected] to September 2017, we will perform a cost and cost-effectiveness analysis of CrAg screening, and continue screening as a routine service at existing sites and expand to additional sites (preferentially to hospitals affiliated with Phase 1 OPCs and to other OPCs whose CD4 testing is conducted at laboratories already conducting CrAg screening as part of Phase 1). CrAg tests will also be made available to screen all patients with  $CD4 \leq 100 \text{ cells}/\mu\text{L}$  including those who are treatment-experienced. The test will also be made available for use among symptomatic patients for diagnostic purposes, including CSF and bloodtesting. We will monitor prevalence at each testing site, but screened patients will not be enrolled in longitudinal follow-up. Phase 2 will last for at least 6 months based on availability of funding and fluconazole for those who screen CrAg positive and the availability/stability of CD4 testing. [Note that follow up of patients enrolled in Phase 1 will continue during this time period, but is considered to be part of Phase 1 rather than Phase 2. Also, sites included in Phase 2 may

change over time as a results of the instability of CD4 testing (e.g., if participating laboratories stop conducting CD4 testing, those sites might no longer be included; if participating laboratories begin CD4 testing for other sites, those sites might be included).]

**Objectives:**

**Primary objectives:**

- To estimate the proportion of people living with HIV (PLHIV) who have advanced disease ( $CD4 \leq 100$  cells/ $\mu L$ ) at presentation to HIV care;
- To determine the prevalence of CrAg-positivity among HIV infected patients with  $CD4 \leq 100$  cells/ $\mu L$  newly enrolled in care in Vietnam;
- To determine clinical outcomes including common causes of mortality for PLHIV with  $CD4 \leq 100$  cells/ $\mu L$  who are enrolled in a programmatic rollout of screening for CrAg;
- To estimate the 12-month mortality among two groups of HIV-infected patients with  $CD4 \leq 100$  cells/ $\mu L$  who are newly enrolled in care and treatment:
  - Those who are CrAg-positive and are treated with high-dose fluconazole
  - Those who are CrAg-negative

**Secondary objectives:**

- To estimate the 12-month retention in care among two groups of HIV-infected patients with  $CD4 \leq 100$  cells/ $\mu L$  who are newly enrolled in care and treatment:
  - Those who are CrAg-positive and are treated with high-dose fluconazole
  - Those who are CrAg-negative
- To identify challenges associated with implementation of routine plasma CrAg screening in clinics providing HIV care.
- To disseminate lessons learned with participating sites to estimate the costs of implementing CrAg screening based on data collected at 22 OPCs participating in Phase 1 and provider costs associated with cryptococcal meningitis (CM) treatment.
- To conduct an incremental cost-effectiveness analysis of CrAg screening compared with a standard of care (SOC)(no CrAg screening, and treatment for symptomatic CM only).
- To project potential cost savings from implementing CrAg screening and financial resources required to implement CrAg screening under different scale-up scenarios and for national rollout. To determine the prevalence *Talaromyces* (formerly *Penicillium*) *marneffei* antigenemia in stored sera and assess the impact of *Talaromyces* antigen (TmAg) positivity on mortality

---

 This objective is part of a sub-study and study procedures related to these objectives have a separate funding source.

**Study participants and sites:**

HIV-positive ART naïve and experienced adults (>18 years of age) with a CD4 count  $\leq 100$  cells/ $\mu$ L or WHO stage 3 or 5 enrolling in HIV care at 22 or more outpatient clinics (see Table 2) in the North, Middle, and South of Vietnam (Phase 1), laboratories serving patients from non-CRICS sites; HIV positive ART-naïve and experienced hospitalized patients who have CD4  $\leq 100$  cells/ $\mu$ L or WHO stage 3 or 4 disease or those with symptoms of CNS infection (Phase 2).

## **1. Introduction**

### **1.1 Background on cryptococcal infection**

CM is a fungal opportunistic infection (OI) that is one of the most common causes of death among human immunodeficiency virus (HIV)-infected persons [1]. In Southeast Asia, the prevalence of CM in HIV-infected patients presenting to care might be as high as 10-20%; an estimated 120,000 cases of CM and 66,000 deaths attributable to CM occur in SE Asia each year; this exceeds mortality from HIV-associated tuberculosis [1]. CM occurs not only before a patient is on antiretroviral therapy (ART), but also afterwards, as an immune

reconstitution inflammatory syndrome (IRIS) [2, 3]. The incidence of CM has declined in some settings for patients who have access to ART [4]. Benefits of ART in patients with HIV will remain suboptimal as long as significant co-morbidities exist. CM is among the significant causes of poor patient outcomes and discontinuation of care. Linkage to care and retention in an ART program in South Africa following an episode of CM was poor, in part because of high rates of mortality[5].

Increasing access to ART, which has resulted in significant reduction in incidence of cryptococcal disease in some settings, has not uniformly reduced overall morbidity and mortality from CM in part due to late HIV testing and treatment and inability to diagnose the disease early. An estimated 17-30% of patients who develop CM do so after the initiation of ART[2, 3, 6], in the context of IRIS.

Screening HIV-infected patients for early cryptococcal disease by detecting circulating cryptococcal antigen (CrAg) and subsequently treating them with fluconazole shows promise as a public health strategy to reduce death and disseminated disease [7], and potentially improve patient retention in care. Studies have demonstrated that CrAg is present in peripheral blood weeks to months before the development of meningitis[8]. Treatment at this stage may be accomplished using oral fluconazole; treatment for meningitis, however, requires a toxic medication (intravenous amphotericin B) with substantial resource utilization (toxicity monitoring, frequent lumbar punctures (LP), and hospitalization). Screening strategies that detect CrAg in blood before clinical meningitis develops have been shown to be highly cost-effective in Cambodia, Uganda, and Vietnam[7, 9, 10]. In 2011, the World Health Organization (WHO) recommended that screening for cryptococcal antigenemia be considered in areas with a high prevalence of cryptococcal disease, among high-risk patients (adults with CD4 counts  $\leq 100$  cells/ $\mu$ L)[11]. As a result, several countries are now investigating the feasibility of implementing CrAg screening as part of HIV care.

## **1.2 HIV and cryptococcal infection in Vietnam**

The HIV epidemic in Vietnam remains concentrated primarily among three key populations: people who inject drugs, men who have sex with men, and female sex workers. As of 30 November 2012, HIV cases had been reported in all 63 provinces of Vietnam, 98% of districts and 79.1% of communes with an estimated 208,866 people living with HIV (PLHIV), 59,839 acquired immunodeficiency syndrome (AIDS) cases, and 62,184 AIDS-related deaths[12].

Data on the overall burden of OIs including CM and mortality in Vietnam is limited. Cryptococcus was reported as the most common OI among HIV-infected persons in a study of patients presenting to a single hospital in Ho Chi Minh City [13]. In that same study, *Cryptococcus neoformans* was the leading cause of fungal meningitis and fungemia and was associated with the highest mortality rate (16.8%) among OIs in HIV patients [13]. In a study in a northeastern province of Vietnam during 2007—2010, two of 49 AIDS-related deaths were attributed to CM[14]. However, the data on prevalence of CM has not been reported.

Only one retrospective study has evaluated CrAg prevalence in Vietnam. There appears to be some geographical variation across different regions; the estimated CrAg-positivity was 6% in the South and 2% in North Vietnam[10]. The prevalence in the middle of Vietnam has not been determined. The reasons for differences in prevalence of cryptococcal disease between regions in Vietnam are not known but could be related to environmental or host factors.

Vietnam is currently undergoing substantial changes in financing for and delivery of HIV services as funding is transitioned from international donors to national government sources. Additionally, as viral load monitoring is being rolled out, CD4 testing is being scaled down. Some laboratories now require patients to pay for CD4 testing, some have reported stock out of CD4 reagents or technical failures. Some laboratories have transitioned CD4 testing to other laboratories.

### **1.3 Diagnosis of cryptococcal infection in Vietnam**

In Vietnam, the diagnosis of CM relies on clinical criteria, a positive cerebrospinal fluid (CSF) India ink stain or a positive CSF culture[15]. However, clinics within Vietnam have variable abilities to conduct LP and CSF analysis. Historically, CrAg tests have not been utilized in countries such as Vietnam, due to cost and need for laboratory infrastructure and training.

In July 2015, the Vietnam MOH released new guidance on HIV/AIDS management which currently recommends cryptococcal antigen screening among ART naïve patients with  $CD4 \leq 100 \text{ cells}/\mu\text{L}$  and pre-emptive therapy with fluconazole for those who are CrAg (+) [16].

### **1.4 Rationale for study**

In Vietnam almost 52.7% of PLHIV who started ART in 2010 had a CD4 count of less than 100 cells/ $\mu\text{L}$ [17], and were therefore at risk of development of severe OIs including CM.

Knowledge of OIs and mortality among patients presenting with late-stage HIV will be useful for clinical care and service delivery. In particular, implementing new prevention strategies for CM are critical to improve the success of HIV treatment programs.

The evaluation of this cryptococcal screening program will provide an assessment of the, survival, other clinical outcomes, and retention in care in of patients with CD4 count  $\leq 100$  cells/ $\mu$ L who test positive and negative for plasma CrAg; an estimate of the prevalence of cryptococcal antigenemia in Vietnam; and also an understanding of clinical outcomes in HIV patients with CD4 count  $\leq 100$  cells/ $\mu$ L.

We hypothesize that implementing plasma CrAg screening in clinics providing routine HIV care will enable identification of Vietnamese adult patients with advanced HIV (CD4  $\leq 100$  cells/ $\mu$ L) who have early cryptococcal disease, enable prompt preemptive treatment with high-dose fluconazole, and improve survival. The program will demonstrate the feasibility. The program will provide important programmatic information and economic data for the scale-up of CrAg screening and treatment in the rest of Vietnam and provide additional information on the burden of OIs and causes of mortality among patients presented with late-stage HIV.

## 2. Study Objectives and Outcome Measures

**Table 1. Study objectives and outcome measures**

Primary objectives	Outcome measures
1. To estimate the proportion of people living with HIV (PLHIV) who have advanced disease ( $CD4 \leq 100 \text{ cells}/\mu\text{L}$ ) at presentation to HIV care	
 
Proportion of HIV-infected adults who have <math>CD4 \leq 100 \text{ cells}/\mu\text{L}</math>
 

2. To determine the prevalence of CrAg-positivity among HIV-infected patients with $CD4 \leq 100 \text{ cells}/\mu\text{L}$	
 
Proportion of patients who are CrAg-positive among all HIV-infected adults who have <math>CD4 \leq 100 \text{ cells}/\mu\text{L}</math>
 

3. To determine clinical outcomes including common causes of mortality for PLHIV with $CD4 \leq 100 \text{ cells}/\mu\text{L}$ who are enrolled in a programmatic rollout of screening for CrAg	
 
Reported causes of death
 
Proportion of patients with HIV-related hospitalizations at 6 and 12 months
 
Proportion of patients with new AIDS-defining OIs/conditions at 6 and 12 months
 

4. To estimate the 12-month mortality among two groups of HIV-infected patients with $CD4 \leq 100 \text{ cells}/\mu\text{L}$ who are enrolled in care and treatment: 
 
Those who are CrAg-positive and are treated with high-dose fluconazole;
 
Those who are CrAg-negative.
 
	
 
Twelve (12) month all-causes and CM-related mortality among patients who screen CrAg-positive and CrAg-negative
 

Secondary objectives	Outcome measures

5. To estimate the 12-month retention in care among two groups of HIV-infected patients with <math>CD4 \leq 100</math> cells/<math>\mu</math>L who are newly enrolled in care and treatment:
 
 
• Those who are CrAg-positive and are treated with high-dose fluconazole
 
• Those who are CrAg-negative
 
	
 
• Twelve (12) month retention among patients who screen CrAg-positive and CrAg-negative
 


6. Identify challenges associated with implementation of routine plasma CrAg screening in clinics providing HIV care
	
 
• Percentage of patients with <math>CD4 < 100</math> cells/<math>\mu</math>L who are lost to follow-up or have incomplete documentation
 
• % of patients with no documented clinic visit 30, 60, and 90 days after date of the scheduled clinic appointment
 

7. To disseminate lessons learned with participating sites
	
 
• Reflection and transition workshop
 

8. To estimate the costs of implementing CrAg screening based on data to be collected at 22 participating OPCs participating in Phase 1 and provider costs associated with CM treatment.
	
 
• Total costs and unit cost per person screened, per CrAg+ treated by site, lab facility type, and cost component
 

9. To conduct an incremental cost-effectiveness analysis of CrAg screening compared with a standard of care (no CrAg screening, and treatment for symptomatic CM only).
	
 
• Incremental cost-effectiveness ratio (cost per CM death averted and cost per quality adjusted life year (QALY))
 

10. To project potential cost savings from implementing CrAg screening and financial resources required to implement CrAg screening under different scale-up scenarios and for national rollout.
	
 
• Total cost savings and amount of financial resources required to implement CrAg screening
 

11. To determine the prevalence of Talaromyces marneffei antigenemia (TmAg) in stored CRICS samples using the Mannose phosphate isomerase 1 (MP1) enzyme-linked immunosorbent assay (ELISA)
	
 
• Proportion of stored samples that test positive for TmAg
 

12. To assess the impact of TmAg positivity on mortality
	
 
• Six (6) and twelve (12) month all-causes and TM-related mortality among patients who screen TmAg-positive and TmAg-negative
 

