## Cryptococcal Retention In Care Study (CRICS)

evaluation **eight weeks later**, during which time a dose reduction in their fluconazole to 200 mg per day maintenance dose will be completed.

- Follow-up visits for fluconazole dose changes should occur 2 weeks after fluconazole initiation and then 8 weeks after. If these do not coincide with routine OPC appointment, then non-routine appointments should be made. Patients should be told the importance of coming back to the OPC at those designated times for fluconazole dose changes. CRICS evaluation will be conducted and follow-up data will be collected at these 2 types of follow-up visits.
- CRICS evaluation and follow-up data collection should also be collected at routinely scheduled OPC visits that occur at ART initiation (if not at one of the above follow up visits), 2-, 6- and 12-months after ART initiation. Therefore, all enrolled CrAg-positive patients will be re-evaluated at 2-week and 10-week after fluconazole initiation and 2-, 6-, and 12-month follow-up after ART initiation (referred to as CRICS's visit). The specific date of these CRICS's visits might be decided in consideration of the patients' regularly scheduled clinic visit. In these visits, a short follow-up form (see Appendix 6: Follow-up ) which incorporates information on current symptoms, side effects of fluconazole (if they are on fluconazole) and other clinical outcomes should be filled out.
- CrAg-negative patients will be re-evaluated at routinely scheduled visits for ART initiation and 2-, 6-, and 12-month follow-up visits. The follow-up data collection form should be filled for each of these visits.
- All visits will be documented using Appendix 18: Patient's visit logbook

Cryptococcal Retention In Care Study (CRICS)

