## Cryptococcal Retention In Care Study (CRICS)

result). Specifically, for CrAg-positive patients, follow-up forms should be filled out at 2-week after fluconazole, 10-week after fluconazole, 2-, 6-, and 12- month follow-ups after ART initiation. Whereas, for CrAg-negative patients, follow-up forms should only be filled out at 2-6-, and 12- month follow-ups after ART initiation. Follow-up patient variables are listed in the section “up. The history of appointment in all patients and history of fluconazole pre-emptive treatment among CrAg (+) patient will be recorded using Appendix and Appendix 19: Fluconazole preemptive treatment log respectively.

- Patients’ quality of life will be re-evaluated at 6- and 12-month follow-ups after ART initiation.
- If a patient requires hospitalization at any point during their 12-month follow-up period, data about hospitalization will be collected in a ‘Hospitalization Form’ (Appendix 7: Hospitalization **Error! Reference source not found.**). The clinical staff at the study site from which the patient is transferred will take charge of collecting these data after the patient has been discharged or died in the hospital (Appendix 11: Off **Error! Reference source not found.**).
- An ‘Off-Study Form’ (Appendix 11: Off **Error! Reference source not found.**) will be used to collect data related to patient’s status, reason for study termination and to assess endpoints.
- All follow-ups will be performed actively, to minimize patient loss to follow-up. Patients will receive a phone call one day before each scheduled visit to remind them of the appointment. These procedures are intended to minimize loss to follow-up and to ascertain patient status in those with a missed study visit at following enrolment into the screening program.

In this amendment, a number of additional items are added to Enrolment Form, Follow-up Form and Off-study Form (health insurance, date of first registration with the OPCs, number of hospitalizations, and source of causes of death report). Such information will be collected prospectively on those who are enrolled after the approved amendment only.

## Phase 2

**For Phase 2:** patients screened for CrAg will be managed by their providers according to the routine OPC procedures, and no additional study related follow-up visits will be conducted. No

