#### **HIV Staging and OIs**

**Current symptoms:** headache, seizures, vomiting, constipation, skin rash, fever, photophobia

**Physical examination:** Glasgow coma score, temperature, weight, neurologic examination, and skin exam, performance status

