# **11. Data Analysis**

## **Data analysis plan:**

### **Primary objectives:**

Proportions will be calculated and presented with associated 95% confidence interval (CI). Clustering effect will be taken into account when calculating 95% CI.

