### AEs

An AE is any undesirable event that occurs to a study participant during the course of the study; that is, from the time of signing the Consent Form until study end (i.e., until the last follow-up visit at 12 months) whether or not that event is considered related to fluconazole or ART.

- Expected AEs:
  - Death due to CM
  - Symptoms of CM
  - Hospitalization for CM
  - Common ARV side effects
  - Death due to other OIs
- Unexpected AEs: Serious unexpected AEs that will be reported including potentially life-threatening reactions attributed to fluconazole and death (see Appendix 9: AE Reporting Form).

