### **Reporting of AEs**

All SAEs and unexpected AEs must be reported to the study team within 2 working days. The study team will review all SAEs urgently to determine expectedness and relatedness. It is the responsibility of the Investigator to request all necessary documentation (e.g., medical records, discharge summary, autopsy) in order to provide comprehensive safety information and to assess whether the risks of study participation have changed.

**Those SAEs that meet all three criteria of Serious, Unexpected, and Related or Possibly Related must be reported to the study team as soon as the event is recognized; the initial report to the IRB will be generated by investigators within 2 working days of site-awareness of the AE (see Appendix 9: AE Reporting Form and Appendix 10A: Clinical Study SAE Reporting ). The information on cases of death will also be captured in database using Appendix 10B: Clinical information for cause of death**

As above, patients will not be monitored prospectively during Phase 2. If the study team happens to learn of any unexpected SAEs that are related or possibly related to CrAg screening in Phase 2, they will be reported to the IRBs.

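### Primary objective 3 fixes new OIs as a crude proportion, with no place for earlier deaths and a poor fit to follow-up that ends before 12 months for about a fifth or more of enrollees

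*Protocol*

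**What the plan says.** Table 1 gives primary objective 3 three outcome measures. One is "Proportion of patients with new AIDS-defining OIs/conditions at 6 and 12 months", one is the matching proportion for HIV-related hospitalizations, and one is "Reported causes of death". For all primary objectives Section 11 states "Proportions will be calculated and presented with associated 95% confidence interval (CI", and adds that the interval allows for clustering. Section 11 names a time-to-event method for deaths only.

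On where OIs are recorded:

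- Section 10.1.2 lists "HIV Staging and OIs" among the follow-up variables.
- Section 10 (Phase 1 Overview) says that "for CrAg-negative patients, follow-up forms should only be filled out at 2-6-, and 12- month follow-ups after ART initiation". Section 7.7 is slightly wider and also has the form completed for CrAg-negative patients at the ART-initiation visit.
- For the other group, Section 7.7 says that "all enrolled CrAg-positive patients will be re-evaluated at 2-week and 10-week after fluconazole initiation and 2-, 6-, and 12-month follow-up after ART initiation".
- Section 10 provides a Hospitalization Form for any admission during follow-up, completed even when the patient dies in hospital, and an Off-Study Form that serves to assess endpoints.
- Section 15 lists "Death due to other OIs" as an expected event and states that "The information on cases of death will also be captured in database using Appendix 10B: Clinical information for cause of death".

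On length of follow-up, the Protocol Summary caps it at 12 months or September 2017, whichever is earlier. Section 3 puts it between 6 and 12 months according to recruitment date.

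**The concern.** The objective concerns every enrolled patient with CD4 at or below 100. In such a cohort some new OIs will be fatal, and the protocol expects this. A proportion read from visit forms at a fixed time answers a narrower question: how many of those who lived and attended had an OI. If the denominator is widened to everyone enrolled but the source stays the visit form, a fatal OI is counted as no OI. In neither case is death treated as an event that ends the chance of a first OI.

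The 12-month figure has a further problem. The study closes on a calendar date, so late enrollees are not observed for 12 months. A crude proportion has no means of using partial follow-up. Section 1.4 intends these results to guide care and service delivery for late presenters, so an OI figure that is too low, or that describes attending survivors only, would mislead the intended users.

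**Working it through.** The protocol states no OI rate, mortality rate or precision for this outcome, so there is no figure to reproduce. Two checks are possible.

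**1. Patients who cannot reach 12 months (from the protocol's own figures)**

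Inputs, from Section 6 unless noted: 957 enrolled by 31 October 2016; about 74 per month (957/13 = 73.6); 1,104 projected at the end of Phase 1; end of follow-up September 2017 (Protocol Summary).

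Twelve months from enrollment are possible only for those enrolled by the end of September 2016.

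- *Projection as stated.* 1,104 − 957 = 147, which is two months of accrual and matches the December 2016 date in the Table 3 row label. Late enrollees are October (74) plus November and December (147) = 221. Share: 221/1,104 = 20%.
- *Enrollment at the same rate to March 2017, the stated end of Phase 1.* Total 957 + 5 × 74 = 1,327. Late enrollees, October to March: 6 × 74 = 444. Share: 444/1,327 = 33%.

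If 12 months runs from ART initiation, as the visit schedule does, the cut-off falls earlier and both shares rise. The 6-month figure is not affected when counted from enrollment, because a March 2017 enrollee reaches six months in September.

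A crude 12-month proportion can treat late enrollees in three ways:

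- Keep them in the denominator. Their unobserved months then count as OI-free, and the figure is too low.
- Keep only patients with a 12-month form. This removes the dead and the lost as well.
- Keep only those enrolled by September 2016. This is valid for the truncation if later enrollees are similar, but it discards 20% to 33% of the cohort at 12 months and still leaves deaths unresolved.

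**2. Effect of fatal OIs (pure illustration; every rate is assumed)**

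Let d be the share who die before an OI is recorded on a visit form, q the share of those deaths with a new OI, s the OI risk in the rest, and c the share of fatal OIs credited from other forms.

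- Proportion counting all OIs: s(1 − d) + qd
- Among form-holders: s, so the shortfall is d(q − s)
- All enrolled, with credit c: s(1 − d) + cqd, so the shortfall is (1 − c)qd

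With d = 10%, q = 50%, s = 20%:

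- All OIs: 0.18 + 0.05 = 23.0%
- Form-holders: 20.0%
- All enrolled, c = 0: 18.0%
- All enrolled, c = 50%: 18.0 + 2.5 = 20.5%
- All enrolled, c = 100%: 23.0%, no shortfall

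Over d = 5–20%, q = 50–80%, s = 10–20%, the form-holder shortfall runs from 0.05 × (0.50 − 0.20) = 1.5 points to 0.20 × (0.80 − 0.10) = 14.0 points. The form-holder figure is too low only when q exceeds s, and the all-enrolled figure has no shortfall at full credit. The width of this range shows that the documents cannot size the effect.

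**The case against.** The strongest reply is that the protocol nowhere limits the OI measure to the Follow-up Form. Section 10 has data abstracted from charts. Section 7.7 collects hospitalization data on patients referred from the baseline visit for an OI that needs admission, which is before ART. The Hospitalization, Off-Study and cause-of-death forms can all hold a fatal OI. If they feed the measure, the numerator bias vanishes. This stands. A reader might infer that OIs are recorded only at visits attended after ART starts, or that fatal OIs certainly drop out. The documents do not support either: there is an ART-initiation visit, there are fluconazole-timed visits, and there are the other forms. Fatal OIs also reach objective 3 through its cause-of-death outcome.

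A reader might also infer that the extra visits of CrAg-positive patients distort OI detection between groups. The OI measure is not defined by CrAg group, and CrAg-positive patients are 2.6% of enrollees (25 of 957), so this does not carry weight.

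A further reply is that the denominator, the source hierarchy and competing-risk methods belong in a statistical analysis plan, which is not at hand. This is right for the denominator and sources taken alone. It does not cover the whole point, because the protocol has itself chosen the estimator: a proportion for this outcome, with time-to-event analysis for deaths only, alongside follow-up that it makes unequal. Finally, Section 6 names two primary outcomes and OIs are neither. The OI measure is an outcome of a primary objective, which moderates its importance without removing the mismatch.

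**Conclusion.** The concern holds in a limited form. The crude proportion suits this outcome badly for two reasons.

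- *Fatal OIs can be missed.* No text says that OIs from the hospitalization, off-study or death forms count. The proportion is understated if they are not credited and OIs are commoner among those who die than among survivors. The size is unknown, and it is zero under full crediting.
- *Unequal follow-up is not handled at 12 months.* Roughly 20% of enrollees on the stated projection, and about 33% if accrual at 74 per month continues to March 2017, cannot have 12 months of observation. This rests only on Section 6 accrual and the September 2017 close, and assumes even monthly enrollment.

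The hospitalization measure shares the second problem and the neglect of death. It is less exposed to the first, because its form covers any admission during follow-up. The change should be made. It does not threaten the study's prevalence estimates.

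**What to change.** In Table 1 and Section 11, define the measure as the cumulative incidence of a first new AIDS-defining OI from enrollment to 6 and 12 months in all enrolled patients. Define the hospitalization measure likewise, as time to first HIV-related admission.

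- Take events from the Follow-up, Hospitalization, Off-Study and cause-of-death forms together.
- Treat death without a new OI as a competing event (Aalen–Johansen estimator). For hospitalization, the competing event is death without an HIV-related admission.
- Censor at last contact, so late enrollees contribute the time they were observed.
- Keep the cluster-adjusted 95% interval.
- Report the proportion with OI or death alongside, and keep causes of death as a separate outcome.
- Show OIs taken from death reports by source, because they are less well confirmed.

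The cost is wording in two places and linkage of forms already collected. No visits, tests or patients are added. Censoring at last contact assumes that patients lost to follow-up resemble those still observed, which the OI-or-death result does not cure and which should be stated.
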